During year 2, a randomized study (3 intervention and 3 control ASPs) will be implemented to test the feasibility of the intervention approach (N=200 youth). A 12-week follow-up, will test the sustained effects of the social climate intervention on ASP PA climate, youth PA affect, cognitions, behaviors, and BMI

Figure 2. Project Timeline

YEAR 1	YEAR 2
April-Sept 2014 - Interviews/Focus Groups - Observations - Intervention development - ASP program recruitment - Hire and Train Staff	Aug-Oct 2015 - Intervention/Measurement Staff Training - Baseline Data Collection (2 ASPs) - Intervention Implement cohort 1
Sept-Dec 2014 - Pilot Baseline Data Collection - Pilot Intervention (1 ASP vs. 1 control)	Oct-Dec 2015 - Baseline Data Collection for cohort 2 (2 more ASPs) - Intervention Implement (cohort 2)
Feb-Apr 2015 - Post-measures in Pilot ASPs - Data cleaning - Hire Project Staff for Y2	Jan-March 2016 - Post-measures for cohorts 1 and 2 - Baseline data collection for cohort 3 (2 ASPs) - Intervention implement (Cohort 3)
April-July 2015 -Data analysis - Revisions to intervention and measurement - ASP Recruitment for Y2	April-May 2016 - Post-measures cohort 3 - Data Management/ Analysis -Manuscript Preparation

Primary Aim 1 (COMPLETED PHASE 1): Interviews/Focus Groups and Youth Survey

Measures. During year 1, we conducted staff interviews (SIs) and youth focus groups (FGs; youth ages 9-14) in ASP sites to assess 1) key physical (e.g., equipment allocation), structural (e.g., PA preferences, activities offered), interpersonal (e.g., peer behaviors), and intrapersonal supports (e.g., social skills) needed to promote and support a social affiliation orientation towards PA (friendship, group belonging, and staff connection goals), 2) program barriers impeding the development and achievement of these social goals, and 3) input on the design and feasibility of initially- developed program components. Through content analysis (NVivo) we identified key themes related to improving social affiliation that were used to inform the development and implementation of the social climate intervention.

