Targeted Population, Recruitment, and Retention. We aim to recruit 8 middle-school ASPs located within a 70 mile radius of Columbia that serve a primarily underserved population of middle school youth (6th-8th grade) youth. All ASP sites will need to include 1 hour of daily PA/freeplay as one component of the curriculum and be similar in size, percentage of youth per site on free or reduced lunch, race, and gender. One ASP will be asked to participate in the pilot during year 1 and will be compared to a school-based control (youth in the control will receive our general health curriculum administered in their health class during the school day). During year 2, six ASPs will be randomized to the treatment or control (general health curriculum) conditions after baseline data collection. ASP staff and all youth enrolled in the program will be asked to participate in the study. To be eligible, youth must 1) be enrolled in the ASP, 2) have parental consent and assent to participate, and 3) be available for baseline and post-intervention measurement. Youth will be excluded from participation only if they have a medical condition that would interfere with the program's prescribed PA.

Overview of Intervention.

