PA Cognitions will be measured by **youth perceptions of their physical ability** (5-pt scale, $M=3.68$; $SD=.97$) and **value of PA** (5-pt scale, $M=3.81$; $SD=1.18$) using four items derived from the expectancy-value model that have been well-validated in youth minority populations⁹²⁻⁹⁴ (reliability coefficients range from .76 to .94). PA Affect will be measured by the extent to which adolescents engaged and enjoyed PA activities using **The Intrinsic Interest Scale**⁹⁵ (reliability coefficients from .83 to .94; 5-pt scale, $M=3.7$, $SD=1.0$) and the degree to which youth are concerned about performing well during PA using the worry subscale of **The Sport-Anxiety Scale-2** (reliability coefficient = .89; test-retest = .90; sum score range 4 to 20; $M= 12.12$; $SD=3.85$).⁹⁶ All PA cognition and affect measures have been shown to be correlated with the SMOSS and other measures of interest to the study (e.g., PA effort, ability).^{23,76,96} **Body Mass Index.** Height and weight will be measured at baseline and post intervention using a Shorr Height Measuring Board and a SECA 880 digital scale. Sex- and age-standardized BMI (zBMI) will be calculated for youth using CDC 2000 reference curves. (See Appendix G for Youth Survey measures).

Covariates. Demographic data will be collected on adolescents at baseline including self-report age (date of birth), race/ethnicity, and gender. Free /reduced lunch status will be derived from school/program records. The Positive Youth Development Scale (PYD-VSF; reliability coefficients from .72 to .90)⁹⁷ and The Strengths and Difficulties Questionnaire (SDQ; test-retest reliability=.80)^{98,99} will be used to measure indicators of positive development (e.g., connection, competence) and the presence of depressive symptoms because of previous research indicating an association between well-being/depression and youth PA and obesity. Lastly, the Self-Regulation Questionnaire- Prosocial (SRQ-Prosocial) assesses individual differences in prosocial behaviors, friendship, interpersonal skills, and exercise (reliability coefficients from .61-.85).¹⁰⁰

E. Analysis Plan

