This proposal is a feasibility test of the social climate intervention and will gauge a plausible effect size of the program for a larger R01 application. To that end, we will examine several subjective and objective markers of program success such as changes in targeted social mechanisms within youth and the ASP climate, and explicit PA outcomes. We will also explore the potential effects of the intervention on youth BMI. Although only minimal change in BMI would be plausible given the length of the current proposal, our findings will have implications for impacting BMI as the targeted outcome of a larger R01 trial.

Primary Aim 1. (ADDRESSED). The first aim of the study is to conduct qualitative interviews with program staff and youth to identify conceptual constructs most relevant for fostering youth PA affiliation orientation. Interviews and focus groups will be transcribed, coded, and analyzed (QSR NVivo) to identify common themes for these study goals. A coding scheme composed of “levels” of categorization or manageable “themes,” will be developed to guide the manner in which the qualitative data will be analyzed. Ultimately, these themes will be used to summarize the data. Data will be coded by two coders and inter-rater reliability estimates will be assessed. Prior to analysis, raters will meet to discuss each coding disagreement until consensus is met regarding final codes. The PI has extensive experience in using QSR NVivo to conduct content analysis of themes (see our previous work).²⁸

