Primary Aim 2. The second primary aim of the study is to assess whether youth in the intervention demonstrate greater change in the 3 PA social affiliation mechanisms from baseline to post-intervention. Gains in these social mechanisms will be assessed with repeated measures ANCOVA models in which time (baseline to end of program and baseline to post-intervention) is a within subject factor and treatment is a between subjects factor for social mechanism variables measured in both conditions. Analyses will control for demographics, baseline BMI, and any other variables for which there are baseline differences between treatment and control groups (e.g., PYD, depression). To examine overall changes in social mechanisms within the intervention alone, similar repeated measures ANCOVAs will be used, with the between subjects treatment factor dropped. The test of interest will be the within subjects factor of time, with affiliation goals expected to improve over time. Process Evaluation, used to assess the quantity (dose) and quality (fidelity) of program implementation, will also serve as feasibility assessments. Our group has extensive experience with “dose-response” analyses.²⁷ Weekly observational assessments of program facilitation, using standardized ratings developed for other studies,¹⁰¹⁻¹⁰³ will be reduced to a total score, indicating overall fidelity to the activity observed.

Secondary Aims. **Secondary Aims 1 and 2** tests the a-priori hypothesis that youth in the intervention (vs. comparison) will have greater improvements in PA affect, cognitions, and MVPA and healthier BMI (z-score) trajectories (e.g., slight reduction; less increase) from baseline to post-intervention. This study will also provide us with information on the effect size that might be expected to power an efficacy trial after completion of the R21 project. Greater improvements will be assessed with several repeated measures ANCOVA models in which time (baseline to post-) is a within subject factor and treatment is a between subjects factor for PA variables measured in both conditions. Analyses will control for demographics (and BMI for PA outcomes) and other variables for which there are baseline differences between treatment and control groups. Multiple imputation protocols^{104,105} will be used to address missing accelerometer data (see our previous work).²⁵

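### An effect size estimated from six randomized ASPs is too imprecise to power the efficacy trial on its own, and the planned ANCOVA, which has no ASP term, would hide this

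*Combined protocol and SAP*

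**What the plan says.** The opening of section E describes a feasibility test that "will gauge a plausible effect size of the program for a larger R01 application". The Secondary Aims paragraph of the same section is more specific about the use: the study is to supply "information on the effect size that might be expected to power an efficacy trial".

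The design behind that estimate is in section D. Under Study Design, "a randomized study (3 intervention and 3 control ASPs) will be implemented to test the feasibility of the intervention approach (N=200 youth". Under Targeted Population, Recruitment, and Retention, "six ASPs will be randomized to the treatment or control (general health curriculum) conditions after baseline data collection". The ASP is therefore the unit of randomization.

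On analysis, the Secondary Aims paragraph says: "Greater improvements will be assessed with several repeated measures ANCOVA models in which time (baseline to post-) is a within subject factor". Treatment is the between-subjects factor, and the covariates are demographics, BMI for the physical activity outcomes, and variables that differ at baseline. No term for ASP appears. The documents give no ICC, design effect, target effect size, power, interval width or other derivation of the 200, and no rule for handling uncertainty in the estimate when the next trial is planned.

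**The concern.** Informing the size of the next trial is a stated yield of this one. An effect size estimated from six clusters has a large standard error, because differences between ASPs do not average out however many youth are measured in each. A chance high estimate would lead to an efficacy trial that is too small. A chance low one would make it needlessly large or appear not worth doing.

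The analysis adds to the problem. A model without ASP treats 200 youth as independently assigned, so its interval is narrower than the design supports. Whoever plans the R01 would see an estimate that looks usable and would have no warning in the output that it is not.

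**Working it through.** The plan has no power or precision figure to reproduce, so the check computes the precision that the design implies.

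**Inputs from the documents.** 200 youth in 6 ASPs, 3 per arm: m = 200/6 = 33.3 youth per ASP, 100 per arm, and 6 − 2 = 4 df between ASPs.

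**Assumptions.** ICC 0.01 to 0.10; two-sided 95% interval; equal cluster sizes; no dropout. The pre-post correlation r is not given, so a range is shown.

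**If ASPs are ignored.** SE = √(2/100) = 0.141 SD. Half-width = 1.96 × 0.141 = 0.28 SD, before any covariate adjustment.

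**If ASPs are respected.** Design effect DE = 1 + (33.3 − 1) × ICC. SE = √[(2/100) × DE × (1 − r²)]. Half-width = 2.776 × SE, where 2.776 is the 97.5% point of t on 4 df. The factor (1 − r²) assumes that baseline adjustment removes variance between ASPs as well as within them, which favours the plan.

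| ICC | DE | SE, r = 0 | Half-width, r = 0 | r = 0.5 | r = 0.7 |
|---|---|---|---|---|---|
| 0.01 | 1.32 | 0.163 | 0.45 | 0.39 | 0.32 |
| 0.05 | 2.62 | 0.229 | 0.64 | 0.55 | 0.45 |
| 0.10 | 4.23 | 0.291 | 0.81 | 0.70 | 0.58 |

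The r = 0 column also applies to a change-score analysis at r = 0.5, since 2(1 − 0.5) = 1. On a scale with SD 1.0, such as the Intrinsic Interest Scale in Study Measures, these half-widths are in scale points. Even at ICC 0 the half-width on 4 df is 2.776 × 0.141 = 0.39. Losing 10 youth (N = 190) barely changes the r = 0 column: 0.46 to 0.81.

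**What this means for sizing a trial.** With 80% power, two-sided 0.05, and before any design effect, n per arm = 2 × (1.96 + 0.842)²/d². This gives 393 for d = 0.2, 175 for 0.3, 63 for 0.5 and 25 for 0.8. In the most favourable cell of the table (ICC 0.01, r = 0.7), an observed 0.30 has the interval 0.30 ± 0.32, or −0.02 to 0.62. That covers planning sizes from 63 per arm at d = 0.5 to 393 at d = 0.2, and without limit as d approaches zero.

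**Risk of an undersized trial.** A trial planned at 80% power on an observed effect has true power below 50% when the observed effect exceeds the true one by a factor of (1.96 + 0.842)/1.96 = 1.43. For a true effect of 0.3 SD the threshold is 0.429. At ICC 0.05, using a normal approximation for the estimate:

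- No baseline gain, SE 0.229: z = (0.429 − 0.3)/0.229 = 0.563, probability about 29%.
- r = 0.5, SE 0.198: z = 0.650, probability about 26%.
- r = 0.7, SE 0.163: z = 0.788, probability about 21.5%.

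The chance of an estimate at or below zero in the same three cases is 9.5%, 6.5% and 3.3%.

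**How well six ASPs estimate the ICC.** An observed ICC of 0.05 corresponds to F = (1 + 32.3 × 0.05)/(1 − 0.05) = 2.75 on 4 and 194 df. Dividing by the 97.5% and 2.5% points of F (2.85 and 0.121) and converting back with (F − 1)/(F − 1 + 33.3) gives a 95% interval of about 0 to 0.40, or design effects from 1 to about 14.

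**The case against.** The strongest reply is that the text promises little. It speaks of gauging a plausible effect and of information on an effect that might be expected, and the aims call the results preliminary. A reader might infer that the plan commits to the point estimate as the planning effect. The documents do not say that. What they do say is that powering the efficacy trial is the purpose, and they set no limit on how the estimate is used.

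The second reply is that the widest range ignores the baseline measurement the plan includes. This is fair, and it is why the range is given for several correlations. Study Measures quotes a test-retest reliability of .90 for the Sport Anxiety Scale-2. If r were 0.9 over the study period, the half-widths would be 0.20, 0.28 and 0.35 SD at ICC 0.01, 0.05 and 0.10. A very stable scale could therefore be estimated tolerably well. The actual pre-post correlation is not given and may well be lower than a test-retest figure. Choosing sites of similar size and demographics may also favour the lower ICCs.

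Two stronger readings should be resisted. One is that the trial cannot tell no effect from a large one. At a half-width of 0.45 or 0.64, an observed effect near zero excludes 0.8 SD, and at ICC 0.01 with r = 0.7 the whole interval is only 0.64 wide. The other is that a low estimate would end a useful program. The protocol judges feasibility on connectedness and affiliation, observed climate, staff readiness, and dose and fidelity. It has no stopping or continuation rule based on a secondary effect size.

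Finally, it would be inconsistent to reject the effect size and then take the ICC from the same six ASPs without caution. That objection stands and shapes the fix.

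**Conclusion.** The concern holds in a limited form. The trial remains sound as a feasibility study, but one of its stated yields is not achievable with useful precision from the estimate alone. Over an assumed ICC of 0.01 to 0.10, the 95% half-width is 0.45 to 0.81 SD with no baseline gain, 0.39 to 0.70 at r = 0.5 and 0.32 to 0.58 at r = 0.7. For most outcomes that is too wide to fix a sample size; a very stable scale may be an exception. The analysis as written would show about 0.28 unadjusted, less than half of the 0.64 that applies at ICC 0.05 on the same basis. The probabilities of an undersized successor apply to a true effect of 0.3 SD at ICC 0.05, and only if that trial were planned on the point estimate. The change should be made, but the concern does not invalidate the trial.

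**What to change.** In the opening of section E and in the Secondary Aims paragraph, replace the effect-size statements with wording to this effect: intervention effects will be reported with 95% confidence intervals that account for ASP (4 df); the point estimate alone will not be used as the planning effect; the efficacy trial will be powered on a justified minimum worthwhile effect; and this trial will supply the SD, pre-post correlation, retention and dose.

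Add that the ICC will be reported with its own interval and combined with values from outside this trial, because six ASPs estimate it poorly.

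The cost is modest. No new sites, measurements or procedures are needed. The intervals must come from an analysis that includes ASP, the stated yield becomes less ambitious, and a minimum worthwhile effect has to be chosen and justified for the efficacy trial's outcome. The documents do not give one, so this involves more than rewording.

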Potential Risks. There is little risk involved in participating in this study. Typical to any Physical Education class (PE) subjects who participate in the intervention may experience some discomfort such as minor physical strains and sprains associated with engaging in physical activities during the intervention. Activities offered in both the health class and the afterschool program are similar in risk to the typical activities offered in the class/afterschool program. There is little risk associated with wearing the accelerometers in the study. Adolescents will be monitored to determine if they are experiencing any discomfort as a result of wearing the devices. There is also little risk to filling out the questionnaires – the majority of questions are centered on PA (social) preferences and perceptions about their experiences in the program, and are not anticipated to trigger negative emotional states. Adolescents will be encouraged to skip a question or stop filling out the questionnaire if they feel any discomfort with questions asked. Numbers will be provided to each adolescent so that their questionnaire cannot be identified, and the names-to-numbers list will be kept separate from participants' recorded responses. The data collected from youth will be kept confidential in all circumstances unless information acquired about a child's wellbeing indicates the child may be at harm. In such a case, we would privately contact the parent and refer the child to the school counselor for further assessment. This breach of confidentiality is articulated in the consent form.

Adequacy of Protection Against Risks

Recruitment and Informed Consent. All program staff from each of the 7 afterschool programs (the health program control administered during the school day in y1 will be excluded) will be asked to participate in the interview component of the study (N=21). Informed consent will be sought from each adult for participation in this project.

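### Multiple imputation is planned for accelerometer data only; survey scales, zBMI and covariates are left to a repeated measures ANCOVA that by default would drop youth with a missing wave or covariate

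*Combined protocol and SAP*

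**What the plan says.** The only missing-data provision closes the paragraph on Secondary Aims 1 and 2 in E. Analysis Plan: multiple imputation "will be used to address missing accelerometer data".

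The other youth outcomes have a model but no missing-data rule:

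- **Primary Aim 2, youth social mechanisms.** "Gains in these social mechanisms will be assessed with repeated measures ANCOVA models". The time points are given in the phrase "in which time (baseline to end of program and baseline to post-intervention) is a within subject factor".
- **Secondary Aims 1 and 2 (affect, cognitions, MVPA, zBMI).** "several repeated measures ANCOVA models in which time (baseline to post-) is a within subject factor".
- **Covariates, Primary Aim 2.** "Analyses will control for demographics, baseline BMI, and any other variables for which there are baseline differences". The examples given for the last group are positive youth development and depression, both measured by questionnaire. The Secondary Aims use a similar list.
- **BMI.** "Height and weight will be measured at baseline and post intervention" (Study Measures).

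F. Human Subjects, Potential Risks, says of the surveys: "Adolescents will be encouraged to skip a question or stop filling out the questionnaire if they feel any discomfort with questions asked". Protection Against Risk repeats this in similar terms.

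The document text gives no item-level scoring rule, analysis population or attrition rate for this trial. Potential Challenges and Alternative Strategies expects no retention difficulty. It cites participation above 95% in earlier work with the same partners, and plans follow-up calls and small incentives.

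**The concern.** A repeated measures ANCOVA with time as a within-subject factor, fitted in the usual way, needs a complete row for each youth: all waves and all covariates. Because imputation is named for one data type only, everything else falls to that default. A missing baseline BMI would remove a youth from the survey models too, since it is a covariate there.

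Two things are at stake. One is precision, because observed waves from partly observed youth are discarded. The other is validity: if the chance of missing a later wave depends on an earlier score, the complete cases are a selected group. This matters because the study's stated purpose is to gauge an effect size for a larger trial. The same survey changes also feed the mediation model of Secondary Aim 3, for which no missing-data method is given either.

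**Working it through.** The plan states no dropout rate and no complete-case number, so there is no figure of its own to reproduce. What follows is illustration.

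**Inputs from the documents.** 200 youth in year 2 (Study Design). Three time points for Primary Aim 2 and two for Secondary Aims 1 and 2 (E. Analysis Plan). Two BMI measurements and a 7-item affiliation scale (Study Measures).

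**Assumed.** A missing rate m per wave of 5%, 10% or 15%, and the dependence between waves.

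**Complete cases.** Independent missingness over k waves gives 200 × (1 − m)^k. If the same youth are missing every time, the number is 200 × (1 − m).

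| m | 3 waves, independent | 2 waves, independent | Same youth each time |
|---|---|---|---|
| 5% | 200 × 0.857 = 171 | 200 × 0.9025 ≈ 180 | 190 |
| 10% | 200 × 0.729 = 146 | 200 × 0.81 = 162 | 180 |
| 15% | 200 × 0.614 = 123 | 200 × 0.7225 ≈ 144 | 170 |

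If baseline BMI is also missing independently at rate m, the three-wave column becomes 200 × (1 − m)^4 = 163, 131 and 104.

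**Precision.** Relative to complete data, the individual-level part of the standard error grows by √(200/n). For n = 171, 146 and 123 this is 1.08, 1.17 and 1.28. A better method recovers only part of that loss, and the between-ASP part of the error is not affected in this way.

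**Item skipping.** This matters only if a scale score needs every item. With an assumed 1% skip rate per item, the 7-item score is lost in 1 − 0.99^7 = 6.8% of administrations. That leaves 200 × 0.99^14 = 174 complete over two waves, or 200 × 0.99^21 = 162 over three.

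**Bias.** A simulation of 150 trials used 100 youth per arm, a true effect of zero, a total SD of about 1 and a within-youth correlation of about 0.56. The third wave was missing with probability 10%, raised to 40% in the intervention arm when the second-wave score was below −0.3. On average 168 youth were complete. Between-arm differences in change from baseline, in SD units:

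| Method | End of program | Last wave |
|---|---|---|
| Complete case | 0.07 | −0.01 |
| Likelihood-based mixed model | 0.00 | −0.01 |

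The complete-case analysis shows a spurious effect at end of program, because youth with low scores at that wave were later removed. At the last wave the two methods agree: in this set-up, selection on the middle score shifts baseline and last wave equally, so their difference is undisturbed.

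**The case against.** Several stronger readings are tempting, and the documents do not support them.

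- **That the plan prescribes listwise deletion.** It does not say so. Dropping incomplete youth is the default of the named model, and an analyst could depart from it.
- **That all of Primary Aim 2 becomes a complete-case analysis.** The aim has four feasibility criteria. Only the first is a youth survey; the others are observed climate, staff readiness, and dose and fidelity.
- **That a youth who skips a question is lost.** This is so only if scoring needs every item. No rule is visible, and Appendix G, which holds the survey measures, is not in the text reviewed. The skip provision is a proper safeguard and is not itself at fault.
- **That one missing wave always removes a youth from Primary Aim 2.** The wording on time can mean one three-wave model or two separate two-wave models. Under the second reading a youth is lost only from the affected model, and the end-of-program bias in the simulation would not arise, since nobody there lacked the first two waves.
- **That the missing youth are the less connected ones, or differ by arm.** This is plausible but conjecture. Even with it built in, the simulated bias was modest and confined to one time point.

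Retention may also be good. Youth usually attend daily, follow-up calls and incentives are planned, and eligibility requires availability at baseline and post-intervention. Absences probably cluster in the same youth, which favours the milder column of the table. These points limit the likely size. They are not an analysis rule, though, and past participation above 95% is not item or wave completeness up to the 12-week follow-up.

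One point about the remedy also stands. For a two-wave outcome, a youth seen only at baseline tells little about change, so a mixed model gains less there, and it does not recover missing covariates.

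**Conclusion.** The gap is real: multiple imputation is limited to accelerometry, and no other section says how missing survey scores, zBMI or covariates will be handled. Under the default behaviour of the named model, the survey and zBMI analyses would be complete-case analyses.

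The loss cannot be derived from the documents. At assumed rates of 5% to 15% per wave, it runs from 10 to 30 of 200 youth if the same youth are missing each time. It runs from about 20 to 56 for two-wave outcomes with independent missingness, and from 29 to 77 for a single three-wave model. Missing covariates would add to it. Bias is possible if missingness depends on earlier scores; its direction and size are unknown. The plan should be changed, but this does not undermine the feasibility study as a whole.

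**What to change.** 1. Analyse the survey and zBMI outcomes with a likelihood-based mixed model that uses every observed wave, and extend the planned multiple imputation to missing covariates, including baseline BMI.
2. Alternatively, extend the imputation to survey scales, zBMI and covariates, with earlier waves, arm and ASP in the imputation model. ASP should enter as a random effect, or as fixed effects in place of arm and cohort, because each ASP belongs to one arm and one cohort and so determines both.
3. State an item-level scoring rule for each scale, and say whether Primary Aim 2 uses one three-wave model or two separate models.
4. Report the complete-case result as a sensitivity analysis.

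The cost is analysis-plan wording and modest analyst time, with no new data. Both routes rely on data being missing at random given what is observed. That assumption cannot be verified and should be stated.
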